10.3. Evaluation of Severity and Causality

10.3.1. Severity

The severity of AEs will be graded according to the following scale:

Mild: Does not interfere in a significant manner with the patient normal functioning level. It may be an annoyance. Prescription drugs are not ordinarily needed for relief of symptoms, but may be given because of personality of the patient.

Moderate: Produces some impairment of functioning but is not hazardous to health. It is uncomfortable or an embarrassment. Treatment for symptom may be needed.

Severe: Produces significant impairment of functioning or incapacitation and is a definite hazard to the patient's health. Treatment for symptom may be given and/or patient hospitalized.

If a laboratory value is considered an AE, its severity should be based on the degree of physiological impairment the value indicates.

Infusion Reactions

The severity of infusion reactions will be graded according to the following scale (semi-colon indicates "or" within description of the grade):

Mild: Mild transient reaction; infusion interruption not indicated; intervention not indicated.

Moderate: Therapy or infusion interruption indicated but responds promptly to symptomatic treatment (eg, antihistamines, NSAIDs, narcotics, IV fluids); prophylactic medications indicated for ≤24 hours.

Severe: Prolonged (eg, not rapidly responsive to symptomatic medication and/or brief interruption of infusion); recurrence of symptoms following initial improvement; hospitalization indicated for clinical sequelae; life-threatening consequences; urgent intervention indicated; death.

Injection Site Reactions

The severity of injection site reactions will be graded according to the following scale (semi-colon indicates "or" within description of grade:

Mild: Pain that does not interfere with activity; mild discomfort to touch; <5 cm of erythema or induration that does not interfere with activity

Moderate: Pain that requires repeated use of non-narcotic pain reliever >24 hours or interferes with activity; discomfort with movement; 5.1 cm to 10 cm erythema or induration or induration that interferes with activity

Severe: Pain that requires any use of narcotic pain reliever or that prevents daily activity; significant discomfort at rest; >10 cm erythema or induration; prevents daily activity; requires ER visit or hospitalization; necrosis or exfoliative dermatitis

10.3.2. Causality

The investigator must provide causality assessment as whether or not there is a reasonable possibility that the drug caused the adverse event, based on evidence or facts, his/her clinical

judgment, and the following definitions. The causality assessment must be made based on the available information and can be updated as new information becomes available.

Include the following when applicable] For double blinded studies using an active comparator, the investigator should consider all study drugs in determining event causality.

The following factors should be considered when assessing causality:

- Temporal relationship: time to onset versus time drug was administered
- Nature of the reactions: immediate versus long term
- Clinical and pathological features of the events
- Existing information about the drug and same class of drugs
- Concomitant medications
- Underlying and concurrent illnesses
- Response to dechallenge (drug discontinuation) or dose reduction
- Response to rechallenge (re-introduction of the drug) or dose increase, when applicable
- Patient's medical and social history

Causality to the study drug (including study drug administration):

• Related:

 The AE follows a reasonable temporal sequence from study drug administration, and cannot be reasonably explained by the nature of the reaction, patient's clinical (eg, disease under study, concurrent diseases, concomitant medications), or other external factors.

or

 The AE follows a reasonable temporal sequence from study drug administration, and is a known reaction to the drug under study or its class of drugs, or is predicted by known pharmacology.

Not Related:

 The AE does not follow a reasonable sequence from study drug administration, or can be reasonably explained by the nature of the reaction, patient's clinical state (eg, disease under study, concurrent diseases, and concomitant medications) or other external factors.

Causality to the study conduct (protocol specified procedure):

• Related:

The AE follows a reasonable temporal sequence from a protocol specified procedure, and cannot be reasonably explained by the nature of the reaction, patient's clinical (eg, disease under study, concurrent diseases, concomitant medications), or other external factors.

Not Related:

 The AE does not follow a reasonable sequence from a protocol specified procedure, or can be reasonably explained by the nature of the reaction, patient's clinical state (eg, disease under study, concurrent diseases, and concomitant medications) or other external factors.

10.4. Safety Monitoring

The investigator will monitor the safety of study patient at his/her site(s) as per the requirements of this protocol and consistent with current Good Clinical Practice (GCP). Any questions or concerns should be discussed with the sponsor in a timely fashion. The sponsor will monitor the safety data from across all study sites. The Medical/Study Director will have primary responsibility for the emerging safety profile of the compound, but will be supported by other departments (eg, Global Patient Safety (GPS); Biostatistics and Data Management). Safety monitoring will be performed on an ongoing basis (eg, individual review of SAEs) and on a periodic cumulative aggregate basis.

10.5. Notifying Health Authorities, Institutional Review Board/Ethics Committee, and Investigators

During the study, the sponsor and/or the CRO will inform health authorities, IECs/IRBs, and the participating investigators of any SUSARs (Suspected Unexpected Serious Adverse Reactions) occurring in other study centers or other studies of the active study drug (REGN4461), as appropriate per local reporting requirements. In addition, the sponsor and/or CRO will comply with any additional local safety reporting requirements. All notifications to investigators will contain only blinded information.

Upon receipt of the sponsor's notification of a SUSAR that occurred with the study drug, the investigator will inform the Institutional Review Board (IRB)/Ethics Committee (EC) unless delegated to the sponsor.

Event expectedness for study drug (REGN4461) is assessed against the Reference Safety Information section of the Investigator's Brochure that is effective for expedited safety reporting.

At the completion of the study, the sponsor will report all safety observations made during the conduct of the trial in the Clinical Study Report to health authorities and IECs/IRB as appropriate.

11. STATISTICAL PLAN

This section provides the basis for the statistical analysis plan (SAP) for the study. The SAP will be revised prior to the end of the study to accommodate amendments to the clinical study protocol and to make changes to adapt to unexpected issues in study execution and data that may affect the planned analyses. The final SAP will be issued before the first database lock.

Endpoints are listed in Section 4. Analysis variables are listed in Section 5.

11.1. Statistical Hypothesis

No formal statistical hypothesis testing will be performed for this study. Based on the sample size, the analysis will be focused on estimation of the treatment effect.

11.2. Justification of Sample Size

The primary objective is to estimate the treatment effect of REGN4461 on glycemic and lipid parameters. The co-primary endpoints are the percent change in TG and change in HbA1c from baseline to week 12 between the placebo and REGN4461 arms in cohort A.

The size of the study is determined by feasibility assessments. Due to the limited number of identified PLD patients with low leptin and moderate metabolic abnormalities, up to 40 patients will be enrolled.

With a total of 40 patients (20 per cohort, randomized in the ratio of 1:1 into the REGN4461 arm and the placebo arm), the primary analysis will be carried out on the 20 patients in the lower leptin cohort A in TP1. The fact that it is unlikely that all of the patients will have HbA1c >7.0%, ie, not all of the patients will be assessed for the HbA1c endpoint, has also been accounted for. From the feasibility work, it is estimated that 78% of the patients will have elevated baseline HbA1c. With 20 patients in cohort A (10 patients per study arm; Table 3), the half-width of the 90% confidence interval in change from baseline to week 12 between the REGN4461 arm and the placebo arm for HbA1c is 1.4 percentage points, assuming the SD of 1.81%. For TG, the half-width of the 90% confidence interval in logarithm transformed geometric mean ratio (GMR) (REGN4461 week12/baseline divided by placebo week12/baseline) is 0.67, assuming the SD for logarithm transformed fasting TG is 0.87. The SD is estimated from the subset samples of the extracted NIH study data.

Table 3: Half-Width of the 90% Confidence Interval for Primary Endpoints

Endpoint	Number of Patients per Group in the Subset	Half of the 90% confidence interval**
HbA1c*	7	1.72%
HbAIC	8	1.59%
HbA1c [†]	10	1.4%
Fasting TG [†]	10	0.67

^{*}Assuming 78% of the patients have elevated baseline HbA1c.

^{**}The estimate of treatment effects for drug for HbA1c are -1.18%, and -52% for fasting TG. After adjusting for placebo effect, the between-group treatment effect estimate for HbA1c are -0.98%, and -47% for fasting TG. Assuming SD for HbA1c is 1.81%, and logarithm transformed fasting TG is 0.87 (SD of HbA1c and fasting TG is extracted from NIH study data).

[†]Assuming all patients have baseline HbA1c >7.0% and TG >200 mg/dL.

11.3. Analysis Sets

11.3.1. Efficacy Analysis Sets

The full analysis set (FAS) includes all randomized patients who received any study drug and have at least 1 post-baseline assessment; it is based on the treatment allocated (as randomized). Efficacy endpoints will be analyzed using the FAS.

11.3.2. Safety Analysis Set

The safety analysis set (SAF) includes all randomized patients who received any study drug; it is based on the treatment received (as treated). Treatment compliance/administration and all clinical safety variables will be analyzed using the SAF.

11.3.3. Pharmacokinetic Analysis Set

The PK analysis population includes all patients who received any study drug and who had at least 1 non-missing result following the first dose of study drug.

11.3.4. Immunogenicity Analysis Set

The ADA analysis set includes all patients who received study drug and had at least 1 non-missing ADA result following the first dose of study drug.

11.4. Statistical Methods

For continuous variables, descriptive statistics will include the following information: the number of patients reflected in the calculation (n), mean, SD, Q1, median, Q3, minimum, and maximum. For categorical or ordinal data, frequencies and percentages will be displayed for each category. Unless otherwise specified, baseline is defined as the last available measurement obtained before the first dose of double-blind study drug.

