FPLD patients are known to suffer from severe hunger, thought to be mediated by leptin deficiency, and this might be improved with REGN4461 treatment. This will be measured using the lipodystrophy hunger questionnaire. In addition to hunger, a number of mental health issues, particularly depression and anxiety have been observed at high rates in lipodystrophy patients (Calabrò, 2020). Regeneron Pharmaceuticals, Inc. (Regeneron) hosted a lipodystrophy patient panel in 2018, consisting mostly of PLD patients, which also identified pain as an important concept to patients. A subsequent interview study with 18 PLD patients also confirmed this feedback. Therefore, to assess whether REGN4461 could impact these patient-centric issues, a number of clinical outcomes assessments (COAs) will be used in this study to assess hunger, pain, QoL, depression and anxiety.

It will be

important to determine whether this potential weight loss is due to loss of adipose tissue, hepatic fat, or muscle mass. For this reason, body composition (whole-body DXA) will be determined at baseline, at the end of TP1 and TP2. The whole-body DXA provides measures of fat mass, lean mass, and bone mass in different regions of interest including arm, legs and trunk. Arm and leg lean mass is predominantly made up of skeletal muscle and is a good proxy for appendicular muscle mass (Kim, 2002) while a large component of trunk lean mass is organs other than skeletal muscle. In addition, patients will have bioimpedance measurements to assess regional fat and lean mass. The purpose of this is to see if bioimpedance may be used as a surrogate for the "gold standard" DXA body composition inclusion criteria in subjects with PLD in future studies.

Rationale for Selected Elements of Study Design

Screening period (up to 10 weeks duration): There is significant heterogeneity in metabolic abnormalities among PLD patients. One study reported a mean fasting TG in FPLD patients of 1058 mg/dL with a SD of 1745 mg/dL (Ajluni, 2017). Fasting TG are also variable from day to

day within individual patients (Bookstein, 1990). Therefore, the protocol allows for multiple visits within the screening period for measurement of fasting TG and the averaging of multiple fasting TG observations will improve the accuracy of the fasting TG estimate in the baseline period. Leptin levels are also known to be variable and will therefore be measured at least twice during the screening period.

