- Initially, 2 measurements of leptin levels will be performed. If the 2 measurements are concordant (fall into the same leptin range: (i) less than 8.0 (ii) greater than or equal to 8.0 and less than or equal to 20.0 (iii) greater than 20.0 ng/mL) the measures will be sufficient to determine patient disposition; if they are discordant, a third measure will be obtained and the arithmetic average of the 3 measures will determine patient disposition. Patients will be assigned to a cohort based on the mean baseline leptin levels (<8.0 ng/mL [cohort A] or 8.0 to 20.0 ng/mL [cohort B]; Section 6.1.1).
- For those patients screened and found eligible under the original protocol, HbA1c and triglycerides assessments will be repeated to reconfirm eligibility of the patient if the screening window of 10 weeks has been exceeded by the time the relevant approvals for Protocol Amendment 1 are in place. Patients screened under the original protocol who do not enter the placebo run-in period within the prescribed visit window will not be considered screen failures, nor will they be considered a deviation provided repeat HbA1c and triglycerides are obtained prior to initiating the placebo run-in as part of Amendment 1. Note: patients who enter screening under the amendment will be

required to adhere to the 10-week screening schedule or it will be considered a deviation.

4-week single blind placebo run-in period (PBO); day -28 to day -1

All patients who meet eligibility criteria will receive placebo by IV infusion on day -28, followed by SC QW injections of placebo starting at day -21. Patients will be observed at least 4 hours after IV infusion to maintain study blinding. Fasting lipid and glucose levels will be collected weekly. Patients will receive training on electronic COA (eCOA) using a device to record COA measures such as hunger, pain, QoL, depression, and anxiety disorders. Patients will undergo baseline body composition by DXA and bioimpedance. Additionally, 2 baseline assessments of liver volume (MRI) and liver fat content (MRI-PDFF) will be performed; the first and second MRI must be performed on separate days.

12-week double-blind placebo-controlled treatment period (TP1); Day 1 until week 12

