Baseline testing occurs in the screening period and the placebo run-in period (see Table 1). After baseline testing, patients in each cohort will be randomized 1:1 to study arm 1 (placebo in TP1 and REGN4461 in TP2) or study arm 2 (REGN4461 in TP1 and TP2), and stratified based on screening HbA1c (HbA1c \leq 7.0% or HbA1c \geq 7.0%) within each cohort.

On day 1, the first dose will be administered IV (mg/kg REGN4461 or placebo) and patients will be observed for at least 4 hours. Starting on day 8, patients will receive matched volumes of SC administered REGN4461 (mg QW) or placebo, respectively, once weekly for a total of 11 SC doses. Fasting blood draws will be taken every 2 weeks according to Table 2.

During the final 2 weeks of TP1, fasting blood draws will be performed weekly (weeks 10, 11, 12). The mean (geometric for TG and arithmetic for all other measures) of these 3 measurements will be taken as the end measure of TP1 and beginning measurement for TP2. Bioimpedance will be assessed during a mandatory in-clinic study visit (week 12). At the end of TP1, patients will undergo liver MRI and whole-body DXA.

12-week single-blind treatment period (TP2); Day 85 until week 24

On day 85 (week 12), patients will receive double-blind dosing in order to maintain blinding to study arm assignment and will then be observed for at least 4 hours:

- Study arm 1: IV loading dose of REGN4461 (mg/kg) followed by SC placebo;
- Study arm 2: placebo IV infusion followed by SC REGN4461 (mg).

Starting at week 13, REGN4461 (mg SC QW) will be administered in a single-blind manner to patients in both study arms (patient remains blinded to treatment allocation). Fasting TG and glucose measurements will occur every 2 weeks through week 20 (Table 2). During the final 2 weeks of TP2, fasting blood draws will be performed weekly (weeks 22, 23, 24). The mean (geometric for TG and arithmetic for all other measures) of these 3 measurements will be taken as the end measure of TP2. Bioimpedance will be assessed during the mandatory in-clinic visit (week 24). At week 24, patients will undergo liver MRI and whole-body DXA.

16-week off-drug safety follow-up period; Day 169 until week 40

This period will be used to monitor efficacy (glycemic, lipid parameters, daily lipodystrophy hunger patient reported outcome [PRO]), safety (hematology, chemistry, urinalysis, vital signs and AEs), PK and PD assessments as REGN4461serum concentrations decline.

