## 5.7.1. Analysis of Primary Efficacy Variables

For the two primary efficacy variables, the primary analyses will be conducted in Cohort A (screening baseline leptin <8.0) for the following patient subgroups:

- Fasting serum TG percent change from baseline to week 12: patients with screening fasting TG >200 mg/dL
- HbA1c absolute change from baseline to week 12: patients with screening HbA1c >7.0%

# 5.7.1.1. Percent Change in Fasting TG from Baseline to Week 12

Percent change from baseline to week 12 in fasting serum TG, will be analyzed in the FAS population for the Cohort A patients with elevated baseline fasting TG >200 mg/dL by using a mixed-effect model with repeated measures (MMRM) approach. The MMRM model will include the following effects: fixed categorical treatment groups (Placebo versus mibavademab), time points (weeks 2, 4, 6, 8, 10, 11, and 12), actual strata (screening HbA1c ≤7.0%, >7.0%), strata-by-time-point interaction, and treatment-group-by-time-point interaction, as well as the continuous fixed covariates of baseline TG value and baseline value-by-time point interaction. Logarithm transformation will be performed to normalize the fasting TG.

Regeneron Pharmaceuticals, Inc.

Page 34 of 88

Protocol: R4461-PLD-20100

Post-baseline data available up to and including the week 12 efficacy analysis window for fasting TG (Table 11 in Appendix 10.2) will be used and missing data are accounted for by the MMRM. Measurements on not-fasting patients will be excluded. Contrast and estimate statements will be used to assess baseline adjusted least-squares (LS) means estimates at week 12 for each treatment group with their corresponding 95% confidence intervals. The LS means at week 12 will be back-transformed into the geometric means to ease clinical interpretation of the result. The difference between the two study treatment groups (mibavademab, placebo) in geometric means will be provided along with its corresponding 95% confidence interval, and nominal p-value.

To support interpretation of the TG results at week 12, descriptive summaries will be provided at each protocol specified DBTP visit. Median percent changes (with Q1 and Q3 bars) will be plotted across visits by treatment group. A spaghetti plot will be provided for individual patient data across visits by treatment group.

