### 6.1. Definition of Baseline for Efficacy/Safety Variables

Unless otherwise specified, the baseline assessment is programmatically defined as the last available measurement prior to the time of the first double-blind study treatment administration. For patients randomized and not treated, the baseline value is defined as the last available value prior to the date of randomization.

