**Table 10: Analysis Windows for Body Weight** 

Visit Label	Targeted DBTP Study Day	Targeted SBTP Study Day	Analysis Window in Study Days	SBTP Analysis Window in Study Days
Screening	< Day 1	N/A	Measurement obtained prior to 1st study trt, and not defined as baseline visit	N/A
Baseline	Day 1	N/A	Measurement obtained closest to 1st study trt	N/A
Week 1	8	N/A	Day 2 to 15	N/A
Week 3	22	N/A	16 to 29	N/A
Week 5	36	N/A	30 to 39	N/A
Week 6	43	N/A	40 to 50	N/A
Week 8	57	N/A	51 to 64	N/A
Week 10	71	N/A	65 to 78	N/A
Week 12	85	N/A	82 to SB Day 1	N/A
Week 14	N/A	SB Day 15	N/A	SB Day 2 to 22
Week 16	N/A	29	N/A	23 to 36
Week 18	N/A	43	N/A	37 to 50
Week 20	N/A	57	N/A	51 to 64
Week 22	N/A	71	N/A	65 to 78
Week 24	N/A	85	N/A	79 to 92
FU- W5	Last study trt admin day + 35 days	Last study trt	Last study trt admin day +15 days TO last study trt admin day + 49 days	
FU-W9	Last study trt admin day + 63 days	Last study trt admin day + 50 days TO last study trt admin day + 77 days		
FU-W13	Last study trt admin day + 91 days	Last study trt admin day + 78 days TO last study trt admin day + 105 days		
FU-W17	Last study trt admin day + 119 days	Last study trt admin day + 106 days TO last study trt admin day + 126 days		

Table 11: Efficacy Analysis Windows for Fasting Triglycerides and Fasting Glucose

Visit Label	Targeted DBTP Study Day	Targeted SBTP Study Day	Analysis Window in Study Days	SBTP Analysis Window in Study Days
Screenin g	< Day 1	N/A	Measurement obtained prior to 1st study trt, and not defined as baseline visit	N/A
Baseline	Day 1	N/A	Measurement obtained closest to 1st study trt while remaining prior to 1st study trt admin	N/A
Week 2	15	N/A	Day 2 to 22	N/A
Week 4	29	N/A	23 to 36	N/A
Week 6	43	N/A	37 to 50	N/A
Week 8	57	N/A	51 to 64	N/A
Week 10	71	N/A	65 to 74	N/A
Week 11	78	N/A	75 to 81	N/A
Week 12	85	N/A	82 to SB Day 1	N/A
Week 14	N/A	SB Day 15	N/A	SB Day 2 to 22
Week 16	N/A	29	N/A	23 to 36
Week 18	N/A	43	N/A	37 to 50
Week 20	N/A	57	N/A	51 to 64
Week 22	N/A	71	N/A	65 to 74
Week 23	N/A	78	N/A	75 to 81
Week 24	N/A	85	N/A	82 to 92
FU- W5	Last study trt admin day + 35 days		Last study trt admin day +15 days TO last study trt admir day + 49 days	
FU- W9	Last study trt admin day + 63 days		Last study trt admin day + 50 d day + 77	
FU- W13	Last study trt admin day + 91 days		Last study trt admin day + 78 d day + 105	
FU- W17	Last study trt admin day + 119 days		Last study trt admin day + 106 days TO last study trt admin day + 126 days	

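### Baseline fasting TG is a single pre-dose draw, although the protocol credits averaging with better baseline accuracy and already collects the draws: a modest, avoidable loss of precision, not a bias

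*Protocol*

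**What the plan says.** **Rationale.** Protocol 3.2.1, in the paragraph on the screening period, notes that fasting TG varies from day to day within a patient and states that "the averaging of multiple fasting TG observations will improve the accuracy of the fasting TG estimate in the baseline period".

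**Collection.** For the placebo run-in, Protocol 6.1 says: "Fasting lipid and glucose levels will be collected weekly". The schedules of events place fasting TG at days -28, -21, -14 and -7, and again on day 1. Protocol 6.1 also says that baseline testing takes place across both screening and run-in.

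**Definition of baseline.** Protocol 11.4: "baseline is defined as the last available measurement obtained before the first dose of double-blind study drug", unless otherwise specified. SAP 6.1: "the baseline assessment is programmatically defined as the last available measurement prior to the time of the first double-blind study treatment administration". SAP Table 11, which is specific to TG and glucose, gives the baseline window as "Measurement obtained closest to 1st study trt while remaining prior to 1st study trt admin". No section specifies a different TG baseline.

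**End of period.** Protocol 6.1 schedules draws at weeks 10, 11 and 12 and says: "The mean (geometric for TG and arithmetic for all other measures) of these 3 measurements will be taken as the end measure of TP1". The same mean starts TP2, and weeks 22 to 24 are treated likewise. The SAP does not carry this out. SAP 5.7 uses one value per window, and Table 11 gives weeks 10, 11 and 12 separate windows.

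**Use of baseline TG.** It is the denominator of the co-primary percent change. It enters the planned TG model through "continuous fixed covariates of baseline TG value and baseline value-by-time point interaction" (SAP 5.7.1.1). It is also the reference for the TG ≤25% stability criterion (Protocol 4.2 and 11.4.3.2, SAP 5.7.2). SAP 1.2.4 now limits the efficacy analysis to descriptive summaries and plots, because the study terminated early.

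**The concern.** The protocol names the problem (day-to-day TG variation), names the remedy (averaging), and schedules the data for it. It then defines the analysis baseline so that only one draw is used. Before treatment, averaging is put into practice only for eligibility, when the first two screening TGs disagree.

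The documents accept the remedy elsewhere. Protocol 6.1 averages three TG draws at the end of each treatment period, and SAP Table 13 builds the hunger-score baseline from a window of day -27 to day 1.

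Two things are at stake. One is the precision of the TG co-primary with at most 10 patients per arm in cohort A. The other is the chance exclusion of Arm 1 patients from the pooled summaries of the first 12 weeks on drug. SAP 5.7.2 requires both stability criteria, so the TG half of the rule also affects who enters the pooled HbA1c summary.

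**Working it through.** **Inputs from the documents.** SD of log TG 0.87; 10 patients per arm; stated 90% CI half-width 0.67 (Protocol 11.2, SAP 2.2); stability limit of 25%.

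**Assumptions.** The within-patient SD of log TG, s, is not given; I use 0.2 to 0.4. Draws are treated as independent around a stable level. Correlated draws would reduce the gain.

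**1. The plan's own figure.** Half-width = t(0.95, 18) × SD × √(2/n) = 1.734 × 0.87 × √(2/10) = 0.675. This agrees with the stated 0.67.

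**2. Half-width with a three-draw baseline.** Read 0.87 as the SD of the log change with one baseline draw, which is how the half-width formula uses it. Averaging k = 3 draws removes s²(1 − 1/3) from the variance: SD = √(0.87² − s² × 2/3).

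| s | SD | Half-width | Narrower by | Equivalent n per arm, 10 × 0.87²/SD² |
|---|---|---|---|---|
| 0.2 | 0.855 | 0.663 | 2% | 10.4 |
| 0.3 | 0.835 | 0.647 | 4% | 10.9 |
| 0.4 | 0.806 | 0.625 | 7% | 11.6 |

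**3. With baseline as a covariate.** Read 0.87 instead as the SD of a single log-TG level, so B² = 0.87² − s². Let d be the SD of the true change (assumed 0.3 to 0.7), m the number of end draws and k the number of baseline draws. Residual variance = B² + d² + s²/m − B⁴/(B² + s²/k). For s = 0.4, d = 0.5, m = 1, the residual SD is 0.732 with k = 1 and 0.677 with k = 3, a cut of 7.5%. Over s = 0.2 to 0.4, d = 0.3 to 0.7 and m = 1 or 3, the cut is about 2% to 15%. Adjustment therefore reduces the loss without removing it.

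**4. Stability rule.** For a patient with no true change, SD of the log ratio = s × √(1/kb + 1/ke), with kb baseline and ke end draws. P(ratio > 1.25) = 1 − Φ(0.2231/SD).

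| Baseline draws | End draws | s = 0.2 | s = 0.3 | s = 0.4 |
|---|---|---|---|---|
| 1 | 1 (SAP) | 21.5% | 30% | 35% |
| 3 | 1 | 17% | 26% | 31% |
| 1 | 3 (Protocol 6.1) | 17% | 26% | 31% |
| 3 | 3 | 9% | 18% | 25% |

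Only upward breaches are counted, following the literal SAP 5.7.2 wording.

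**5. Noise in the two Arm 1 periods, in units of s.**

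| Rule | TP1 change | TP2 change |
|---|---|---|
| SAP: all single draws | √2 = 1.41 | √2 = 1.41 |
| Protocol 6.1 end values, one-draw baseline | √(4/3) = 1.15 | √(2/3) = 0.82 |
| Three-draw baseline only, single end draws | √(4/3) = 1.15 | √2 = 1.41 |
| Three draws at every point | √(2/3) = 0.82 | √(2/3) = 0.82 |

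**The case against.** The last pre-dose value is a coherent choice, stated consistently in both documents, in a study that tests no formal hypothesis. The averaging sentence sits in the screening-period paragraph, and the averaging carried out there serves eligibility. Both points are fair. Still, the sentence names the baseline period, Protocol 6.1 extends baseline testing into the run-in, and the reason given applies equally to the analysis baseline.

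A reader might infer several stronger things that the documents do not support:

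- **That the comparison is biased.** Baseline precedes the first double-blind dose and allocation is randomized, so a noisy baseline costs precision and leaves more chance imbalance, but it does not favor an arm.
- **That precision improves by 18% or 29%.** Those are 1 − √((4/3)/2) and 1 − √((2/3)/(4/3)), the cuts in the day-to-day component alone with one or three end draws. Measured against the total SD of 0.87, the gain for s of 0.2 to 0.4 is 2–7%.
- **That the Arm 1 periods are compared with unequal noise.** This follows from Protocol 6.1's end values. Under the SAP's single-draw windows the two periods are equal, and changing the baseline alone would make them unequal.
- **That the run-in draws serve no efficacy purpose.** They supply the last available value if day 1 is missing or not fasting.
- **That one odd day-1 draw would move the group result.** The planned TG plot shows medians with quartiles, which resist a single outlier. Individual percent changes and spaghetti plots do carry it in full.

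Early termination also makes the covariate argument largely moot. It works both ways, though: descriptive percent changes have no adjustment to absorb baseline noise.

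**Conclusion.** The point holds as a modest matter of efficiency. The plan uses one draw for baseline TG when its own reasoning and schedule support an average, and no TG-specific exception is stated.

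The cost is a half-width of 0.675 where about 0.66–0.63 was available, and a stability rule that excludes more truly stable patients than it need. The three-draw baseline removes roughly 3 to 5 percentage points of chance breaches with the SAP's single week-12 value, and about 6 to 8 points with three-draw end values. Much of the misclassification remains in either case.

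These sizes rest on the assumed within-patient SD of 0.2 to 0.4, on independent draws, and on reading 0.87 as the SD of the log change. The stability figures matter only if the pooled first-exposure summaries are still produced under the reduced scope in SAP 1.2.4, which does not settle that.

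**What to change.** - In Protocol 11.4, SAP 6.1 and SAP Table 11, define baseline fasting TG as the geometric mean of the available fasting draws at days -14, -7 and 1 pre-dose. Use it for percent change, the model covariate and the stability rule.
- In the SAP, take the geometric means of weeks 10–12 and of weeks 22–24 as the end-of-period TG values, as Protocol 6.1 already prescribes. The two changes belong together, so that the Arm 1 TP1 and TP2 changes carry equal noise.
- Show the last-value baseline as a sensitivity summary.
- Declare the baseline change in SAP 1.2.4.

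The cost is derivation rules only, since every draw is already scheduled. The downside is that baseline then spans the last two weeks of the run-in and could include some residual enrollment effect, which the run-in exists to absorb (Protocol 3.2.1). Leaving out days -28 and -21 limits this, and the sensitivity summary would help show whether it matters.
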